***ADA response endpoints:***

- An **ADA positive patient** is defined as a patient with at least one treatment-induced or treatment-boosted ADA positive sample at any time during the on-study observation period

- **ADA incidence** is defined as the number of ADA positive patients among evaluable patients divided by the number of evaluable patients.
- **ADA prevalence** is defined as the sum of the number of patients with preexisting ADA and the number of patients with treatment induced ADAs, divided by the number of evaluable patients.

## **2.1.7 Biomarker endpoints**

### **2.1.7.1 Receptor density**

CD38 RD will be assessed from bone marrow aspirates at the screening.

### **2.1.7.2 Immune genetic determinants**

Immune genetic determinants in peripheral blood plasma samples will be assessed at Cycle 1 Day 1.

### **2.1.7.3 Immune phenotyping**

Immune phenotyping in bone marrow (screening) and/or peripheral blood (Cycle 1 Day 1 and Cycle 3 Day 1) will be assessed.

### **2.1.7.4 Soluble CD38**

Soluble CD38 levels in peripheral blood plasma samples will be assessed at Cycle 1 Day 1.

## **2.1.8 Quality-of-life endpoints**

Not applicable

## **2.1.9 Health economic endpoints**

Not applicable

## **2.1.10 Further therapy after discontinuation of investigational medicinal product administration during the study**

Further therapies after discontinuation of IMP will be assessed.

## **2.2 DISPOSITION OF PATIENTS**

This section describes patient disposition for both patient study status and the patient analysis populations.

Screened patients are defined as any patients who signed the informed consent. A listing of screening failure patients (screened patients who were not treated with isatuximab) and reason for screening failure (when available) will be provided.

The number and percentage (when applicable) of patients in each of the following analysis population will be provided:

- All treated/safety population
- Pharmacokinetics population
- ADA evaluable population

For all above categories (except for the all treated population) percentages will be calculated using the number of patients in the all treated population. For the all treated population, no percentages will be calculated.

For patient study status, the number and percentage of patients in each of the following categories will be provided using the all treated/safety population:

- Patients off treatment and reasons for treatment discontinuation
- Patients on treatment at time of the analysis cut-off date

Major deviations potentially impacting efficacy/safety analyses include:

- No prior treatment with IMiD and PI (for  $\geq 2$  cycles or  $\geq 2$  months of treatment)
- Was not refractory to the most recently received both IMiD and PI included therapy
- Did not achieve an MR or better to all prior lines of therapy

All critical or major deviations will be summarized in a table giving numbers and percentages of patients with deviations. Protocol deviation will also be listed.

### **2.2.1 Randomization and drug dispensing irregularities**

Not applicable, as this is non-randomized study.

## **2.3 ANALYSIS POPULATIONS**

### **2.3.1 All treated/safety population**

The all treated/safety population will include all patients who have given their informed consent and who have received at least one dose (even incomplete) of isatuximab.

This population is the primary population for the analyses of efficacy and safety parameters. All analyses using this population will be based on the treatment actually received.

### **2.3.2 Pharmacokinetic population**

The PK population will include patients from the safety population who receive at least 1 dose of isatuximab even if incomplete, with data for at least isatuximab concentration available post-baseline.

### **2.3.3 ADA evaluable population**

The ADA evaluable population will include all treated patients with at least one ADA assessment with a reportable during the ADA on-study observation periods

## **2.4 STATISTICAL METHODS**

### **2.4.1 Demographics and baseline characteristics**

Continuous data will be summarized using the number of available data, mean, standard deviation, median, minimum, and maximum for each treatment group. Categorical and ordinal data will be summarized using the number and percentage of patients.

Parameters described in [Section 2.1.1](#) will be summarized using descriptive statistics.

Past medical or surgical history other than multiple myeloma will be summarized by SOC (sorted by internationally agreed order) and PT (sorted by alphabetical order) for the all treated population.

### **2.4.2 Prior or concomitant medications (other than anticancer therapies)**

Prior and concomitant medications will be presented for the all treated population.

Medications will be summarized according to the WHO-DD, considering the first digit of the anatomical therapeutic chemical (ATC) class (anatomical category) and the first 3 digits of the ATC class (therapeutic category). All ATC codes corresponding to a medication will be summarized, and patients will be counted once in each ATC category (anatomical or therapeutic) linked to the medication. Therefore, patients may be counted several times for the same medication.

The table for prior and concomitant medications will be sorted by decreasing frequency of ATC followed by all other therapeutic classes. In case of equal frequency regarding ATCs, alphabetical order will be used.

#### ***Pre-medications***

Number (%) of patients with pre-medications (antihistamine, corticosteroids, h2 blocker, and acetaminophen) will be summarized by each administration in cycle 1.

### 2.4.3 Extent of investigational medicinal product exposure and compliance

The extent of IMP exposure will be assessed and summarized within the all treated population (Section 2.3.1).

The dose information will be assessed by the following variables.

- Number of cycles started
- Duration of isatuximab exposure (or time on-treatment) in weeks is defined depending on the isatuximab administration schedule as follows:
  - If treatment is discontinued at a cycle with QW isatuximab administration: [date of last dose of isatuximab + 7 days – date of first dose of isatuximab] / 7.
  - If treatment is discontinued at a cycle with Q2W isatuximab administration: [date of last dose of isatuximab + 14 days – date of first dose of isatuximab] / 7.
- Actual dose in mg/kg: for a given cycle and day of administration, the actual dose in mg/kg corresponds to the actual dose in mg administered at this time point divided by the actual body weight as measured at each time point
- Cumulative dose in mg/kg: the cumulative dose is the sum of all actual doses of isatuximab, expressed in mg/kg, given from first to last administration
- Actual dose intensity (ADI) in mg/kg/week: defined as the cumulative dose (in mg/kg) divided the duration of isatuximab exposure (in weeks)
- Relative dose intensity (RDI) in %:  $100 \times \text{ADI (mg/kg/week)} / \text{Planned Dose Intensity (mg/kg/week)}$

Planned dose intensities corresponds to the planned dose (mg/kg) received at Day 1 of cycle 1, multiplied by the theoretical total number of doses during the started cycles (count 2 for Q2W and 4 for QW), divided by the theoretical cycle duration expressed in weeks (i.e., 4 weeks), regardless of dose/schedule changes (as defined in the protocol section 6.5). ADI and RDI will be calculated separately in cycle 1 and subsequent cycles respectively, due to the difference of administration interval.

Total number of cycles started, number of cycles started by patients as a quantitative variable and by category (i.e., number [%] of patients receiving at least 1 cycle, at least 2 cycles...), duration of isatuximab exposure, cumulative dose, ADI, RDI, and RDI by category (< 80%, [80 - 105%],  $\geq 105\%$ ) will be summarized by descriptive statistics.

The following variables will be computed to describe dose delays and interruption:

- Cycle delayed is defined as follows:
  - A cycle is deemed as delayed if the start date of the current cycle - 28 - start date of the previous cycle is  $> 3$  days. Cycle delay is not defined for the first cycle.
- Infusion delay (within a cycle, excluding day 1): within cycle 1, an infusion is deemed to be delayed if start date of the current administration – start date of previous administration – the theoretical duration (which is 7 days) is  $\geq 3$  days. For subsequent cycles ( $\geq$ cycle 2),

an infusion is deemed to be delayed if start date of the current administration – start date of previous administration – the theoretical duration (which is 14 days) is  $\geq 4$  days

- Dose interruption: A dose will be considered to be interrupted if the isatuximab administration is temporarily stopped during an infusion and then restarted (typically in case of Grade 2 IARs).
- Dose reduction: Although not allowed in the study protocol, potential dose reductions will be screened and reported in the clinical study report. The first administration will not be counted as a dose reduction. For the second and subsequent isatuximab administrations, dose reduction will be determined using the dose level intervals provided in [Table 5](#), by comparing the current dose level to the previous dose level. If the current dose level is not within the same dose level interval as the previous dose level, then the current dose level is considered reduced.

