6.5 DOSE DELAYS/ MODIFICATIONS

In this study, Cycle 1 consists of 4 isatuximab administrations and consecutive cycles consist of 2 isatuximab administrations.

A dose delay of up to 2 weeks is permitted in order for a patient to recover to their baseline status (see [Section 6.4](#)) or to accommodate scheduling issues (eg, holidays, weather, etc.). In case of a delay greater than 2 weeks the patient will be withdrawn from the treatment as per the investigator and the Sponsor decision. Exceptions allowed by the investigator and the Sponsor should be considered only for patients with clear objective clinical benefit.

Intra-patient dose and schedule modifications are not allowed.

6.6 GUIDELINES FOR MANAGEMENT OF ADVERSE EVENTS:

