13.4.2 Extent of Investigational Medicinal Product Exposure

The extent of investigational product exposure will be assessed and summarized within the all treated population.

The following dose information will be summarized descriptively (N, Mean, Standard deviation, Median, Min, and Max).

- Duration of study treatment exposure: defined as day 1 of last cycle date – first dose date + 28 days, regardless of unplanned intermittent discontinuations.
- Cumulative dose: The cumulative dose is the sum of all doses from first dose to last isatuximab administration.
- Actual dose intensity (ADI): defined as the cumulative dose divided by the number of weeks on study (duration of study treatment exposure divided by 7).
- Relative dose intensity (RDI): defined as the ratio of the actual dose intensity to the planned dose intensity. The RDI is an indicator of the feasibility of the chosen schedule of administration.

The number and its percentage of people who correspond to the following condition will be calculated.

- Infusion delay: Within Cycle 1, an infusion is deemed to be delayed if start date of the current administration – start date of previous administration is >9 days. For subsequent cycles (\geq Cycle 2), an infusion is deemed to be delayed if the time interval between 2 infusions is >17 days (ie. >3 days compared to the theoretical duration between 2 infusions).
- Dose interruption: administration of isatuximab treatment is temporarily stopped during the infusion.

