### 2.4.3 Extent of investigational medicinal product exposure and compliance

The extent of IMP exposure will be assessed and summarized by dose level cohort within the all treated population ([Section 2.3.1](#)).

The dose information will be assessed by the following variables.

- Number of cycles started
- Duration of isatuximab exposure (or time on-treatment) in weeks: defined as  $\{\min(\text{date of last dose of isatuximab} + X \text{ days, date of death}) - \text{first dose date}\} / 7$  (X equals to 7 in cycle 1 and 14 in the subsequent cycle). The theoretical duration of a cycle is 28 days
- Actual dose in mg/kg: for a given cycle and day of administration, the actual dose in mg/kg corresponds to the actual dose in mg administered at this time point divided by the actual body weight as measured at each time point
- Cumulative dose in mg/kg: the cumulative dose is the sum of all actual doses of isatuximab, expressed in mg/kg, given from first to last administration
- Actual dose intensity (ADI) in mg/kg/week: defined as the cumulative dose (in mg/kg) divided the duration of isatuximab exposure (in weeks)
- Relative dose intensity (RDI) in %:  $100 \times \text{ADI (mg/kg/week)} / \text{Planned Dose Intensity (mg/kg/week)}$

Planned dose intensities corresponds to the planned dose (mg/kg) received at Day 1 of cycle 1, multiplied by the theoretical total number of doses during the started cycles (count 2 for Q2W and 4 for QW), divided by the theoretical cycle duration expressed in weeks (i.e., 4 weeks), regardless of dose/schedule changes (as defined in the protocol section 6.5). ADI and RDI will be calculated separately in cycle 1 and subsequent cycles respectively, due to the difference of administration interval.

Total number of cycles started, number of cycles started by patients as a quantitative variable and by category (i.e., number [%] of patients receiving at least 1 cycle, at least 2 cycles...), duration of isatuximab exposure, cumulative dose, ADI, RDI, and RDI by category (< 80%, [80 - 105%),  $\geq 105\%$ ) will be summarized by descriptive statistics.

The following variables will be computed to describe dose delays and interruption:

- Cycle delayed is defined as follows:
  - A cycle is deemed as delayed if the start date of the current cycle - 28 - start date of the previous cycle is  $> 3$  days. Cycle delay is not defined for the first cycle.

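### Both SAPs, section 2.4.3: planned dose intensity divides the doses of all started cycles by one 4-week cycle, and the dose-reduction rule also flags increases

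*SAP*

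**What the plan says.** Section 2.4.3 is the exposure section of both the Phase 1 and the Phase 2 SAP. Each takes planned dose intensity as the planned dose at Cycle 1 Day 1 times "the theoretical total number of doses during the started cycles (count 2 for Q2W and 4 for QW), divided by the theoretical cycle duration", and gives that duration as 4 weeks. Actual dose intensity (ADI) is cumulative dose over weeks of exposure. RDI is 100 x ADI / planned intensity, reported also in three categories: below 80%, 80 to 105%, and 105% or more. Both add that "ADI and RDI will be calculated separately in cycle 1 and subsequent cycles respectively".

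The protocol has no formula for planned intensity. Section 13.4.2 defines RDI only as the ratio of actual to planned intensity and says: "The RDI is an indicator of the feasibility of the chosen schedule of administration". Section 6.5 gives the administrations per cycle: "Cycle 1 consists of 4 isatuximab administrations and consecutive cycles consist of 2 isatuximab administrations".

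For dose reduction, both SAPs compare each infusion after the first with the one before it. If it is "not within the same dose level interval as the previous dose level, then the current dose level is considered reduced". Table 5 of each SAP sets the intervals: above 0 to 15 mg/kg, and above 15 to 25 mg/kg.

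Exposure duration is written for treatment as a whole. The Phase 2 SAP closes it according to the cycle in which treatment stops (its first rule begins "If treatment is discontinued at a cycle with QW isatuximab administration"). The Phase 1 SAP uses last dose plus X days, capped at death, where "X equals to 7 in cycle 1 and 14 in the subsequent cycle". Protocol 13.4.2 has a different definition: Day 1 of the last cycle minus the first dose date, plus 28 days.

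**The concern.** In the planned-intensity formula the two halves of the fraction cover different spans. The dose count is a total over the started cycles, while the time is one cycle. The split between Cycle 1 and later cycles does not remove the mismatch, because all later cycles are still pooled. A programmer who follows the sentence literally gets a planned intensity that grows with time on treatment. The patients who stay longest then show the lowest RDI, which is the reverse of what a feasibility indicator should show.

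The dose-reduction sentence has no direction. A change to a higher interval meets it as well as a change to a lower one, so a return to full dose is recorded as a reduction.

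There is also a lesser gap. RDI is wanted for Cycle 1 alone, but no end of the Cycle 1 period is written for a patient who goes on to Cycle 2.

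**Working it through.** The documents state no numerical dose intensity, so there is no figure to reproduce. The check applies the written formulas to illustrative patients; none of the sequences or delays is trial data.

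**Planned intensity.** Inputs: 20 mg/kg (the Cohort 2 level in Protocol 6.2.1); four doses in Cycle 1 and two in each later 28-day cycle (Protocol 6.5); ADI and RDI as in SAP 2.4.3. Dose and duration are taken within the period concerned, as the separate calculation implies.

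- Cycle 1: 20 x 4/4 = 20 mg/kg/week. With a single cycle the formula is right.
- k later cycles, every dose on time: cumulative dose is 20 x 2k = 40k mg/kg. The last dose plus 14 days closes a period of 4k weeks, so ADI = 40k/4k = 10.
- Literal planned intensity: 20 x 2k/4 = 10k, so RDI = 100 x 10/(10k) = 100/k %.
- Per-cycle count: 20 x 2/4 = 10, or equivalently 20 x 2k/(4k) = 10, so RDI = 100% for every k.

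| Later cycles k | Literal planned intensity (mg/kg/week) | RDI, literal | RDI, per-cycle count |
|---|---|---|---|
| 1 | 10 | 100% | 100% |
| 2 | 20 | 50% | 100% |
| 3 | 30 | 33.3% | 100% |
| 5 | 50 | 20% | 100% |
| 10 | 100 | 10% | 100% |

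From k = 2 the literal formula puts a fully dosed patient below 80%. At 10 mg/kg both intensities halve and the RDI values are the same.

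**Dose reduction.** Inputs: the Table 5 intervals. The first infusion is never flagged, but it is the comparator for the second.

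| Sequence (mg/kg) | Flagged as written | Flagged if a lower interval is required | Patient counted as reduced: as written / with direction |
|---|---|---|---|
| 12, 20, 20, 20 | infusion 2 | none | yes / no |
| 20, 20, 12, 20, 20 | infusions 3 and 4 | infusion 3 | yes / yes |

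**End of the Cycle 1 period.** Four full doses of 20 mg/kg on schedule give 80 mg/kg, and planned intensity is 20. Let Cycle 2 start d days late (Protocol 6.5: "A dose delay of up to 2 weeks is permitted").

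- Last Cycle 1 dose + 7 days: 80/4 = 20, RDI 100% for any d.
- Cycle 2 Day 1: RDI = 28/(28 + d), which is 80.0% at d = 7 and 66.7% at d = 14.
- The Protocol 13.4.2 definition applied to Cycle 1 alone, a fixed 28 days: RDI 100% for any d.

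If the Day 22 dose is missed and Cycle 2 starts on time, the three give 60/3 = 20 (100%), 60/4 = 15 (75%) and 60/4 = 15 (75%).

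**The case against.** The strongest reply is that nobody would program the literal formula. The counts 2 and 4 are per-cycle counts and match Protocol 6.5. The divisor is called a cycle duration. The sentence speaks of intensities in the plural, which fits the split by period. An RDI of 10% for a fully dosed patient after ten later cycles would be noticed in any dry run. This stands as evidence of intent, and the per-cycle count is the probable meaning. It does not make the sentence consistent, since the words calling for a total over the started cycles remain and no other section gives a formula.

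On dose reduction, the label itself implies a fall, and Protocol 6.5 does not allow dose modification within a patient. The tables count only patients with at least one reduction, so a fall followed by a return changes no reduction count, only a flag in the listing. The count is wrong only when a patient's sole change is upward. The infusion-reaction guidance in Protocol 6.6.1 makes that uncommon: Grade 3 or 4 reactions end treatment, and an interrupted dose is to be completed the same day. All of this stands and limits the size of the point.

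On the Cycle 1 period, the SAP rules extend naturally to last Cycle 1 dose plus 7 days, although they are attached to overall exposure. A reader might infer that the SAPs are wrong here and that Cycle 1 should run to Cycle 2 Day 1 so that a late start is counted. The documents do not support that. The protocol's own definition gives a third answer, and cycle delays are already tabulated by patient and by cycle. Ending at Cycle 2 Day 1 is also uneven: a patient who misses Day 22 scores 75% on continuing on time, but 60/3 = 20, or 100%, on stopping after Day 15 under last dose plus 7 days.

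**Conclusion.** Two rules are wrong as written in both SAPs. The planned-intensity sentence mixes a total over cycles with the length of one cycle; taken literally it gives RDI 100/k % and the below-80% category from the second later cycle. The dose-reduction sentence flags rises as well as falls; it can miscount a patient whose only change is upward, and otherwise adds a false flag to the dosing listing. The missing end of the Cycle 1 period is a clarification only.

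A reader might infer that the exposure tables will show RDI falling as 100/k. The documents do not support that as an expected result, because the per-cycle count is the probable intent; the figures show what the wording permits. Nor is efficacy touched: ORR, its test, alpha and sample size do not use these variables. Cycle delays and incomplete infusions are also reported separately. Severity is minor. The RDI figures assume on-time full dosing, with dose and duration taken within the same period.

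**What to change.** In section 2.4.3 of both SAPs:

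1. State planned intensity as planned dose x 4/4 per week for Cycle 1 and planned dose x 2/4 per week for later cycles. Equivalently, divide the total dose count by 4 weeks times the number of started cycles in the period.
2. Count a dose as reduced only if it lies in a lower interval than the previous dose.
3. As a secondary clarification, state one end of the Cycle 1 period for ADI and RDI, and reconcile it with the duration definition in Protocol 13.4.2. No particular end date is proposed here.

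The cost is a few sentences in each SAP and about one line of programming per derivation. No new data are needed, and no dose or treatment rule changes.

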**Table 5 - Dose reduction criteria**

Actual dose level	Dose level interval
Dose level 1 (10 mg/kg)	$>0$ mg/kg and $\leq 15$ mg/kg
Dose level 2 (20 mg/kg)	$>15$ mg/kg and $\leq 25$ mg/kg

- Infusions not completed: patients who received less than 90% of the planned dose at an infusion.

Dose delay and interruption will be analyzed at the patient, cycle, and total number of isatuximab administration levels as follows:

- Patient level
  - Number of patients
  - Number (%) of patients with at least 1 dose reduction
  - Number (%) of patients with at least 1 dose interruption
  - Number (%) of patients with at least 2 infusions interrupted
  - Number of patients who could have a cycle delayed (patients who received  $\geq 2$  cycles, used for % calculation in this section):
    - Number (%) of patients with at least 1 cycle delayed
      - Number (%) of patients with a maximum cycle delayed between 4 and 7 days
      - Number (%) of patients with a maximum cycle delayed  $> 7$  days
    - Number of patients who could have an infusion delay (patients who received  $\geq 2$  infusions, used for % calculation in this section).
      - Number (%) of patients with at least 1 infusion delay.
- Cycle level
  - Number of cycles administered (used for % calculation for this level)

- Number (%) of cycles delayed
  - Number (%) of cycles delayed with a maximum delay between 4 and 7 days
  - Number (%) of cycles delayed with a maximum delay on > 7 days
- Total number of isatuximab administration level
  - Total number of isatuximab administration (used for % calculation for this level)
  - Number (%) of isatuximab administration interrupted
  - Number (%) of isatuximab infusions interrupted more than once
  - Number of infusion interrupted at (with % calculated using the total number of infusions interrupted): 1st infusion, 2nd infusion, subsequent infusions.
  - Time from infusion start to first interruption in minutes (quantitative (descriptive statistics) and qualitative: <5, 5–10, 11–30, 31–40, 41–50, 51–60, 61–90, 91–120, >120), missing.
  - Number (%) of infusions not completed (patients who received less than 90% of the planned dose).

Duration of infusion is defined as the time from the start (date/time) of infusion to the end (date/time) of infusion. It will be summarized with descriptive statistics for first and subsequent infusions. A listing of dosing data will be provided and include the following variables, number of cycles started, cycle-day, start date, cycle delayed, actual dose in mg/kg, dose interruption, dose reduced and dose not complete.

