8.1.2 Dose of Drug per Administration

Isatuximab will be administered once every week (QW) in Cycle 1 (4 weeks) followed by once every other week (Q2W) in subsequent cycle until unacceptable toxicity, disease progression, withdrawal of consent and/or Investigator's decision ([Section 1.2](#)). Cycle N day 1 corresponds to cycle N-1 day 29.

For dose level and schedule, refer to [Section 6.2.1](#).

The initial rate of infusion of isatuximab will be 175 mg/hour.

- First infusion:
Initiate infusion rate at 175 mg/hour. In the absence of infusion associated reaction after 1 hour of infusion, increase the rate by 50 mg/hour increments every 30 minutes, to a maximum of 400 mg/hour.
- Subsequent infusions:
Initiate infusion rate at 175 mg/hour. In the absence of infusion associated reaction after 1 hour of infusion, increase the rate by 100 mg/hour increments every 30 minutes, to a maximum of 400 mg/hour.

recovered, the infusion may be restarted at one half of the original infusion rates. If symptoms do not recur after 30 minutes, the infusion rate may be increased in 50 mg/hour increments every 30 minutes, to a maximum of 400 mg/hour.

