- Infusion delay: within cycle 1, an infusion is deemed to be delayed if start date of the current administration - start date of previous administration - the theoretical duration (which is 7 days) is  $\geq 3$  days. For subsequent cycles ( $\geq$ cycle 2), an infusion is deemed to be delayed if start date of the current administration - start date of previous administration - the theoretical duration (which is 14 days) is  $\geq 4$  days
- Dose interruption: A dose will be considered to be interrupted if the isatuximab administration is temporarily stopped during an infusion and then restarted (typically in case of Grade 2 IARs).
- Dose reduction: although not allowed in the study protocol, potential dose reductions will be screened and reported in the clinical study report. The first administration will not be counted as a dose reduction. For the second and subsequent isatuximab administrations,

dose reduction will be determined using the dose level intervals provided in [Table 5](#), by comparing the current dose level to the previous dose level. If the current dose level is not within the same dose level interval as the previous dose level, then the current dose level is considered reduced.

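### Cycle-level delay percentages in both SAPs count Cycle 1, which cannot be delayed, and the Phase 1 infusion-delay rule measures Cycle 2 Day 1 against 14 days when 7 are scheduled

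*SAP*

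**What the plan says.** **Cycle delay (Section 2.4.3 of both SAPs).** A cycle is delayed if it starts more than 3 days beyond 28 days after the start of the previous one, and "Cycle delay is not defined for the first cycle". The results are then tabulated at two levels, with different kinds of denominator:

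- Patient level: "Number of patients who could have a cycle delayed (patients who received" at least 2 cycles).
- Cycle level: "Number of cycles administered (used for % calculation for this level"). The splits for delays of 4 to 7 days and of more than 7 days sit under this same denominator.

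**Infusion delay.** For Cycle 2 onward, the Phase 1 SAP takes the start date of the current infusion, subtracts "start date of previous administration - the theoretical duration (which is 14 days"), and flags a result of 4 days or more. It makes no exception for Day 1. Within Cycle 1 the interval is 7 days and the threshold 3 days. Protocol Section 13.4.2 has the equivalent rule, a gap of more than 17 days from Cycle 2 on, also without an exception. The Phase 2 SAP limits its scope: "Infusion delay (within a cycle, excluding day 1").

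**Schedule.** Cycle 1 infusions fall on Days 1, 8, 15 and 22. Protocol Section 8.1.2 adds: "Cycle N day 1 corresponds to cycle N-1 day 29".

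**The concern.** In (a), every treated patient adds one Cycle 1 to the denominator that can never enter the numerator. The patient-level rows of the same list keep only those who could have the event, so one principle is applied at one level and dropped at the next.

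In (b), the change from weekly to two-weekly dosing takes effect after Cycle 2 Day 1, not before it. The Phase 1 rule switches to the 14-day interval one infusion too early. The protocol's own gloss, that more than 17 days means more than 3 days beyond the theoretical interval, is not true of this infusion.

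Both faults can only lower the figures they touch. What is at stake is the accuracy of the reported description of schedule adherence. In a Phase 1 cohort of 3 to 6 patients, all counted in the row, one misclassified patient moves the infusion-delay percentage by 1/6 = 17 to 1/3 = 33 percentage points. The Phase 1 and Phase 2 infusion-delay rows also share a name but not a scope.

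**Working it through.** The plan states no delay rate, so there is no figure to reproduce. The check is arithmetic on the definitions.

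**(a) Cycle-level denominator.** Let n be the number of treated patients, m the mean number of cycles per patient and D the number of delayed cycles.

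- Reported rate = D / (n·m).
- Rate among cycles that can be delayed = D / (n·m − n) = D / (n·(m − 1)).
- Ratio of the two = (m − 1) / m.

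The documents do not give m, so the values below are assumptions. The 20% is an illustration, not a forecast.

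| m (assumed) | (m − 1)/m | Rate reported if the at-risk rate is 20% |
|---|---|---|
| 2 | 0.50 | 10.0% |
| 3 | 0.67 | 13.3% |
| 5 | 0.80 | 16.0% |
| 10 | 0.90 | 18.0% |
| 20 | 0.95 | 19.0% |

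The ratio is below 1 for every m, so any non-zero rate is understated, most of all when patients stop early. The splits by length of delay shrink by the same factor.

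**(b) Cycle 2 Day 1 in Phase 1.** The scheduled gap is 29 − 22 = 7 days. With Cycle 1 given on schedule, a dose L days late has a gap of 7 + L days and starts Cycle 2 L days late. The corrected rule below keeps the 4-day threshold.

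| Days late (L) | Gap | Gap − 14 | Phase 1 infusion flag (≥4) | 7-day interval, flag if gap − 7 ≥ 4 | Cycle delay (>3) |
|---|---|---|---|---|---|
| 0 | 7 | −7 | no | no | no |
| 3 | 10 | −4 | no | no | no |
| 4 | 11 | −3 | no | yes | yes |
| 10 | 17 | 3 | no | yes | yes |
| 11 | 18 | 4 | yes | yes | yes |

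The infusion rule therefore misses delays of 4 to 10 days, and the cycle-delay variable flags every one of them. With the 3-day threshold that applies within Cycle 1, a dose 3 days late would also count as missed. The protocol's limit of more than 17 days gives the same flags as the Phase 1 SAP. At 17 days the excess over schedule is 17 − 7 = 10 days, not 3.

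From Cycle 3 on, Day 1 falls 29 − 15 = 14 days after the previous Day 15, so the 14-day interval is right there. The fault is confined to Cycle 2 Day 1.

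**The case against.** **The cycle-level denominator is disclosed and the loss is recoverable.** The row is labelled openly, and a reader can rebuild the at-risk rate as delayed cycles divided by (cycles administered − patients treated). This stands as mitigation. The protocol also uses total cycles as the by-cycle denominator for adverse events and laboratory data (Sections 13.4.4.2 and 13.4.4.4). That parallel does not help, because those events can occur in Cycle 1.

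**A reader might infer that Phase 1 conceals late Cycle 2 doses.** The documents do not support that. A Cycle 2 start at least 4 days late is a delayed cycle under the Phase 1 SAP, and one more than 7 days late falls in its own row. The dosing listing shows start dates and cycle delays. If an adverse event caused the delay, it also enters the table of events leading to dose delay. Only the infusion-delay row is affected, and only for a patient with no other flagged infusion.

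**A reader might infer that these rates carry the case for feasibility or tolerability.** Protocol Section 13.4.2 gives the feasibility role to relative dose intensity. DLTs have their own criteria in Section 9.1.1, including a treatment delay of more than 14 days, which is not taken from these rows. Even the rule as written would flag such a delay at Cycle 2 Day 1: 15 days late is a gap of 22 days, and 22 − 14 = 8.

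**A reader might infer that delay rates in general are understated.** The patient-level cycle-delay rate has the right denominator, and the Phase 2 infusion-delay rule does not apply the 14-day interval to Day 1.

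**Conclusion.** The point holds as a correction to two descriptive summaries, and it is minor. For (a), the direction is certain in both SAPs whenever any cycle is delayed. The size depends on mean cycles per patient: half the at-risk rate at an assumed mean of 2, nine tenths at 10. For (b), the fault lies in the Phase 1 SAP and protocol Section 13.4.2. It leaves Cycle 2 Day 1 doses 4 to 10 days late out of one patient-level row, assuming Cycle 1 ran on schedule and the 4-day threshold is kept. Neither part bears on dose-escalation decisions or on the test of ORR.

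**What to change.** 1. In Section 2.4.3 of both SAPs, make the cycle-level denominator for delay the number of cycles from Cycle 2 onward, splits included. The total number of cycles administered can stay as a separate count.
2. In the Phase 1 infusion-delay definition, use a 7-day theoretical interval for Cycle 2 Day 1 and say which threshold applies. Four days agrees with the ±3-day visit window for Day 1 of later cycles in the protocol's flowchart footnotes and with the cycle-delay rule. Align protocol Section 13.4.2.
3. If the Phase 2 wording that excludes Day 1 is adopted instead, state that Day 1 delays are reported only through the cycle-delay variable. The two options are not interchangeable. Excluding Day 1 also drops Day 1 delays from Cycle 3 on, which the present rule counts correctly, so the infusion-delay count may fall. The 7-day option can only raise it or leave it unchanged.
4. If the two phases keep different scopes, footnote the infusion-delay rows as not comparable.

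The cost is a few lines of text and code. No new data are needed. Any non-zero cycle-level percentage will rise.
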